# **6.2.4** Management of SAEs

1214 Any SAE must be treated immediately with appropriate therapeutic measures.

# 1215 **6.2.5 Follow-up of SAEs**

- When a SAE occurs, subjects must be followed up until complete clinical recovery and normalization of laboratory test results, or until their condition is stabilized. Follow-up
- 1218 information must be recorded on the SAE follow-up form and reported to the regulatory
- authority, ethics committee and sponsor.
- 1220 If at any time after discontinuation of the IMP there is a SAE that comes to the attention of the
- investigator, and the investigator believes that there is a reasonable probability that the SAE is
- caused by the IMP, it should be reported to the sponsor and the ethics committee.

# 6.2.6 Disease progression

1223

- Progression of the disease refers to the deterioration of the subject's condition by the disease
- being studied. Progression of the disease includes an increase in the severity of the disease being
- studied and/or an increase in the symptoms of the disease. In this trial, events clearly attributed to
- disease progression should not be reported as AEs.

# 1228 6.3 Report of AEs/ SAEs /Suspected Unexpected Serious Adverse Reaction (SUSAR)

- Each AE should be assessed to see if it meets the criteria for a SAE. If a SAE occurs, it should be
- reported in accordance with relevant regulations.

# 1231 **6.3.1 Report of Serious Adverse Events**

- Except for SAEs that are not required to be reported immediately as specified in the trial protocol
- or other documents (e.g., investigator's brochure), the investigator should immediately report all
- 1234 SAEs in writing to the sponsor, and should subsequently provide a detailed, written follow-up
- report in a timely manner. Serious adverse event reports and follow-up reports should indicate
- the subject's identification code for the clinical trial, rather than the subject's real name, civil
- identification number, and residential address and other identifying information. The AEs
- important for safety evaluation and laboratory outliers, which are specified in the trial protocol,
- should be reported to the sponsor in accordance with the requirements and timeframe of the trial
- 1240 protocol.
- For reports involving death events, the investigator should provide other required data, such as
- autopsy reports and final medical reports, to the sponsor and the ethics committee.

- 1243 The investigator should sign and read the relevant safety information of the clinical trial provided
- by the sponsor in a timely manner upon receipt and consider the treatment of the subjects,
- whether to adjust accordingly, and communicate with the subjects at the earliest possible time if
- necessary, and the SUSAR provided by the sponsor should be reported to the ethics committee.

# 6.3.2 Suspected Unexpected Serious Adverse Reaction Reporting Requirements

- 1248 The sponsor should timely report to the Center for Drug Evaluation information of SUSAR and
- other potential serious safety risks that occurs during the clinical trial in accordance with the
- relevant requirements. According to the severity of safety risks, the sponsor can be required to
- take measures to adjust the drug clinical trial protocol, informed consent form, investigator's
- brochure and other measures to strengthen risk control. If necessary, the sponsor can be required
- to suspend or terminate the drug clinical trial.
- The sponsor should report adverse drug reactions in accordance with the requirements and
- timelines. Upon receipt of safety-related information from any source, the sponsor should
- immediately analyze and assess it, including the severity, relevance to the IMP and whether it is
- an expected event, etc. The sponsor should expeditiously report SUSAR to all investigators
- participating in the clinical trial as well as to the sites and the ethics committees; the sponsor
- should report SUSAR to the National Medical Products Administration and the health
- 1260 authorities.

1247

- Expedited reporting to the Center for Drug Evaluation according to the nature (category) of the
- 1262 SAE in accordance with the following timeframes:
- 1263 (i) For fatal or life-threatening unexpected serious adverse reactions, the applicant should report
- as soon as first informed, but not more than 7 days. And report and complete the follow-up
- information within the following 8 days.
- Note: The day the applicant is first informed is day 0.
- 1267 (ii) For non-fatal or life-threatening unexpected serious adverse reactions, the applicant should
- report as soon as possible after first informed, but not more than 15 days.
- 1269 Expedited reporting of other potentially serious safety risk information can be emailed to:

# SAE and Other Safety Information Reporting Requirements

	SAE	SUSAR	Other potentially serious safety risk information	Periodic Safety Update Report
Reporter	Investigator	The sponsor	The sponsor	The sponsor
Report Recipient	Sponsor Ethics (Death event only)	The site/ Ethics Committee/The Center for Drug Evaluation	Investigator Ethics Committee The Center for Drug Evaluation	Investigator Ethics Committee The Center for Drug Evaluation
Time limit	Immediate (no specific time limit)	CDE corresponds to a expedited reporting time limit of 7/15 days. Not specified for the other department.	Expedited reporting by mail is available. [contact]	Once a year or as specified by CDE, not specified by other departments

#### 1272 **6.3.3 Death**

1281

- All deaths that occur during the study period or during the follow-up period following the IMP administration as specified in the clinical trial protocol must be reported as follows:
- When it's confirmed that the death is caused by disease progression, it should be reported to the study monitor during the next monitor visit and should be recorded in the eCRF, but not as a SAE.
- Unexplained deaths should always be reported as SAEs. An autopsy may help assess the cause of death. If an autopsy is performed, a copy of the autopsy report should be forwarded to the sponsor's pharmacovigilance team or its representative within reasonable time frame.

# 6.3.4 Non-serious adverse event reporting requirements

All AEs must be recorded under the corresponding item on the AEs page /eCRF. Please note that
the adverse event information collection form and AEs CRF are two different forms. When
collecting same information, the forms must be filled in consistently. For example, the same
adverse event term should be used on both tables. AEs should be reported in concise medical
terms on both the CRF and serious adverse event information collection form.

#### 6.3.5 Pregnancy

1287

1288

1289

1290

1291

1297

- To ensure the safety of the subject, each pregnancy and pregnancy outcome of the subject treated with the trial must be reported to the sponsor using a corresponding pregnancy report form within 24 hours after being informed. Abnormal pregnancy outcomes should be considered as SAEs and reported using a table of SAEs.
- Pregnancy is not considered as an adverse event unless it is suspected that the IMP may affect the effectiveness of the contraceptive. Congenital malformations/ birth defects and spontaneous abortion should be reported and treated as SAEs. Selective abortion without complications will not be treated as an adverse event. All pregnancy outcomes (spontaneous abortion, elective abortion, ectopic pregnancy, normal production, or congenital anomalies) should be followed up
- If any pregnancy event occurs during the study, the investigator or other person in the site should report the incident to the appropriate sponsor representative within 24 hours of the event being known.
- Access to pregnancy outcome information should also follow the same time requirements.

and recorded, even if the subject has withdrawn from the study.

- The following CRF modules should be used for reporting: use the pregnancy reporting template in the CRF to report pregnancy events and use the pregnancy outcome reporting template to report pregnancy outcomes.
- Pregnancy events that occur within 6 months of the end of the study should also be reported to the sponsor.

# 1307 STUDY TERMINATION AND SUBJECT WITHDRAWAL

Version 1.1 / Jul 29, 2020 *confidential* Page 61 of 91

#### 7.1 Study Termination

- The termination of the study means that the clinical study has not been completed according to the protocol, and all studies are stopped in the middle. The primary purpose of the study termination is to protect the rights of the subjects, or to ensure the quality of the study, or to avoid unnecessary economic losses. Early termination of clinical trials should be promptly notified to the investigating parties. The termination of the study includes the following:
- 1314 (1) Serious safety problems are found during the study, and the study needs to be terminated after the drug safety committee and the investigator jointly evaluate;
- 1316 (2) The IMP is found to have no clinical value during the study;
- 1317 (3) During the study, it is found that there are major errors in the design of the protocol, it is
  1318 difficult to evaluate the drug, or there is a major deviation in the implementation of the
  1319 protocol, which affects the final evaluation of the drug, and the study should be suspended;
- 1320 (4) The sponsor requests to stop the study (such as funding reasons, management reasons, etc.);
- 1321 (5) The drug regulatory authority orders the study have to stop for some reason.

# 1322 **7.2 Subject Withdrawal**

# 1323 7.2.1 Withdrawal Determined by Investigator

- The investigator decides to withdraw subjects from the study, including following situations:
- 1325 (1) There are some complications or special physiological changes in the subjects during the study, which are not suitable for further study;
- 1327 (2) Poor compliance of subjects, which affect safety and efficacy evaluation;
- 1328 (3) Subjects who have SAEs and are not suitable to continue the study;
- 1329 (4) Other circumstances that the investigator determines require withdrawal from the study.
- 1330 The proposed indication of TBN is ALS, which is a progressive disease with the possibility of
- disability and death. The withdrawal criteria for ALS patients with significant deterioration of the
- 1332 condition are set, and the rescue treatment measures are improved as follows:

- Protocol No.: MP-2019-004
- 1333 1) The patient cannot swallow or come to the hospital for visits, affecting administration and
- routine follow-up, the investigator decides whether the subject withdraws from the trial, and
- follows up regularly until the end of the study.
- 1336 2) The patient has respiratory failure and relies on a ventilator to maintain ventilation (≥ 22 h
- per day for  $\ge 10$  days), which may endanger their life, continuing the trial may affect the
- patients' life safety, and the investigator decides whether the subject withdraws from the
- 1339 trial.

- 1340 3) To protect the subjects, when they have respiratory failure or other emergency situations, the
- department should have the ability to deploy emergency treatment personnel and equipment,
- and use ventilators and other rescue equipment in time, and open the green treatment
- 1343 channel of the department when needed.
- 1344 4) The patient has a serious adverse event or the condition worsens to the point of endangering
- their life. To protect the subject and respect their wishes, the investigator can consider letting
- them withdraw and receive more treatment after assessing their survival status, and follow
- up until the end of the study.

#### 7.2.2 Withdrawal Decided by Subject

- According to the provisions of the informed consent form, subjects have the right to withdraw
- from the study halfway, or not receive the IMP or test, or be lost to the visit (also referred to as
- withdrawal, or drop-out). The reason for withdrawal should be known and recorded. If subjects
- withdraw from the study due to AEs or abnormal laboratory test results, this important and
- special event and its test results should be recorded on the electronic case report form (eCRF).
- For a subject who drops out of the study or drops out of follow-up, the investigator should take
- active measures to complete the last examination as much as possible, so as to analyze the
- efficacy and safety of the patients. The cause of drop-out should be documented in detail, safety
- and efficacy data for the subject should be available to the extent possible, and all end-of-study
- evaluations should be conducted with subject consent and compliance. All case data should be
- kept integrally for reference. Subjects who sign informed consent forms and have been randomly
- assigned in groups cannot be replaced.

# 1368 STATISTICAL ANALYSIS

- Statistical analysis will be carried out under the authorization of the sponsor. The following
- sections describe the statistical methods used for the efficacy and safety analysis of this study. A
- detailed description will be provided in the Statistical Analysis Plan (SAP).
- All statistical analyses will be programmed using SAS 9.4 or higher version software. All
- statistical tests will be performed on a two-sided test.  $P \le 0.05$  will be considered statistically
- significant, and the confidence interval is 95% confidence.

# 1368 **8.1 Sample Size Estimation**

- The trial is an exploratory study of safety and efficacy, no statistical assumptions will be made
- and no sample calculations.
- This study is expected to enroll a total of 150 subjects, with 50 in each group.

#### 1372 **8.2** Analysis Population

- 1373 This study used three data sets: Full Analysis Set, Per-Protocol analysis set, and Safety analysis
- 1374 set.
- 1375 Full Analysis Set (FAS): A collection of all randomized subjects with at least one study
- administration and at least one valid post-dose efficacy evaluation data. FAS is the primary
- analysis set. The FAS will be used to analyze the subject's distribution, demographic data, and
- 1378 baseline characteristics and efficacy. Subjects will be analyzed according to their randomized
- 1379 groups.
- Per-Protocol Set (PPS): It included FAS subjects who meet the main inclusion criteria and do not
- meet the main exclusion criteria, complete the treatment without any major protocol deviations.
- The PPS is mainly used for the sensitivity analysis of efficacy.
- Safety analysis set (SS): A collection of subjects with at least one administration and actual
- safety data of the post study administration. Missing safety values are generally not carried
- forward. SS will be used for safety analysis. Subjects will be analyzed according to randomized
- 1386 groups.

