# **Secondary Endpoints:**

✓ Difference between the groups in the proportion of events such as death, tracheotomy, invasive ventilation, or continuous non-invasive ventilation ( $\geq 22$  h per day for  $\geq 10$  days);

	✓ Difference between the groups in gripe strength change from baseline at Day 180;
	✓ Difference between the groups in respiratory function (%FVC) change from baseline at day 180;
	✓ Difference between the groups in ALSAQ-40 scores change from baseline at Day 180.
	Safety evaluation including: adverse events (AEs), serious adverse events (SAEs), clinical laboratory tests (hematology, urinalysis, blood biochemistry, thyroid function), vital signs (blood pressure, respiratory rate, pulse and body temperature), 12-lead electrocardiogram (ECG) examination, physical examination.
	Primary safety indicators:
Safety Assessment Indicators	Percentage of subjects with serious adverse reactions within 180 days; (Adverse reactions: AEs related to the IMP)
	Secondary safety indicators:
	Percentage of subjects with adverse reactions within 180 days;
	AEs, SAEs, and their incidence, the clinical manifestations, severity, time of occurrence, end time, duration, treatment measures and outcomes of these are to be recorded, and the correlation between AE and IMP are to be determined.
PK/PD and Biomarkers	The cerebrospinal fluid (Tmax after administration, optional) is to be taken (in part of subjects) at baseline period before administration and 180 days after administration, and the concentration of TBN and its metabolites in cerebrospinal fluid and plasm are to be measured for PK/PD analysis. Biomarkers, such as 3-NT, 8-OHdG, NFL levels in cerebrospinal fluid are to be determined.
Treatment	Subjects need to terminate the treatment permanently if the following events occur:
Termination Termination	✓ The subject is pregnant;
	✓ The subject withdraws informed consent;
	✓ The subject has a medical emergency that requires to terminate the

	treatment permanantly, such as death, tracheotomy, invasive ventilator assisted ventilation, or continuous non-invasive ventilator assisted ventilation (≥ 22 h per day for ≥10 days);  ✓ The subject has a medical emergency requiring a unblinding of the treatment of the subject;  ✓ Determinations based on medical reasons made by investigator.

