# **3.5.3.1 Time of Clinic Visit**

- Subjects will be followed up at the study center at day  $30 \pm 3$  (V2), day  $90 \pm 7$  (V4), and day 180
- 718  $\pm$  7 (V7) after randomization. During the course of the trial, the investigator may increase the
- visit depending on the patient's condition, and record in the medical record form.

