#### **3.5.3.2 Items of Clinic Visit**

- Each clinic visit should evaluate and record the occurrence of AEs, concomitant medication,
- dispense IMP and return the unused IMP, and dispense and return of diary cards.
- 723 V2, V4: weight, ALSFRS-R score, grip strength, respiratory function (%FVC), vital signs,
- 724 physical examination, electrocardiogram, hematology, urinalysis, blood biochemistry, urine
- 725 pregnancy, and thyroid function will be test.
- 726 V7: Weight, physical examination, vital signs, hematology, urinalysis, blood biochemistry,
- 727 thyroid function, 12-lead electrocardiogram, respiratory function (%FVC), grip strength,
- 728 ALSFRS-R scale, ALSAQ-40 scale, centralized blood collection (if consent), cerebrospinal fluid
- 729 collection (if consent), and urine pregnancy in women of childbearing age.

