# **3.5.4.2 Items of phone Visit**

- 736 The visits (V1, V3, V5 and V6) will be to inquire and teach about treatment compliance in
- 737 addition to documenting AEs and concomitant treatments (medication & non-medication). On
- days  $60 \pm 3$  (V3),  $120 \pm 3$  (V5), and  $150 \pm 3$  (V6), subjects will be encouraged to follow up in
- the hospital, where vital signs, physical examination, and weight will be recorded. If the subject
- unable to the hospital, family will be required to the hospital at the scheduled visit to collect new

medication and diary cards. The post-study visit will take within 2 weeks of the end of the trial.

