# 1412 8.3.4 Analysis of Secondary Efficacy Endpoint

- 1413 The following four secondary efficacy endpoints, the continuous data of each visit in different
- groups will be described using mean  $\pm$  standard deviation and median (minimum, maximum).
- 1415 Comparing with the baseline data, the paired T test is to be used to compare the within-group
- before-after differences. Analysis of variance (ANOVA) is to be used before and after treatment
- between groups. For the first secondary endpoint (endpoint event and disease exacerbation
- event), Kaplan-Meier plots will be used to describe the survival rate of patients without endpoint
- event, and Log-Rank test or non-parametric statistical method is to be used to compare the
- indicators of each group.
- 1421 (1) Proportion of endpoint events, including death, tracheotomy, invasive ventilator-assisted
- ventilation, or continuous non-invasive ventilator-assisted ventilation ( $\geq$  22 h per day for  $\geq$
- 1423 10 days);
- 1424 (2) Difference between the groups in grip strength change from baseline at Day 180;
- 1425 (3) Difference between the groups in respiratory function (%FVC) change from baseline at
- 1426 Day 180;
- 1427 (4) Difference between the groups in ALSAQ-40 scores change from baseline at Day 180.
- 1428 **8.3.5 Safety Assessment**
- Descriptive statistical analysis is mainly to be used to list the AE and SAE, drug-related AE and
- SAE that occurs in this trial, and between-group comparisons are conducted using the  $X^2$  test or
- 1431 Fisher's test.
- 1432 Descriptive statistics are to be used to summarize laboratory tests, vital signs, and
- electrocardiograms, etc. Shift tables are to be used to describe changes in normal/abnormal
- results before and after administration, such as laboratory tests, electrocardiograms, and physical
- 1435 examinations.
- 1436 **8.3.6 Interim Analysis**
- 1437 Not Applicable

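### The only full efficacy set requires a post-dose efficacy evaluation, so a subject who dies or is lost before the first assessment can be left out of the death/ventilation analysis

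*Protocol*

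**What the plan says.** **Analysis set.** Section 8.2 defines three sets. FAS membership needs randomisation, a dose and a later measurement: "administration and at least one valid post-dose efficacy evaluation data. FAS is the primary" set. It serves disposition, demographics, "baseline characteristics and efficacy. Subjects will be analyzed according to their randomized" groups. The per-protocol set is a subset of the FAS, and the safety set is assigned to safety only.

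**Event endpoint.** The synopsis lists as the first secondary efficacy endpoint: "Difference between the groups in the proportion of events such as death, tracheotomy, invasive ventilation, or continuous non-invasive ventilation". Section 8.3.4 repeats it ("Proportion of endpoint events, including death, tracheotomy, invasive ventilator-assisted" ventilation and so on) and sets the method: for this endpoint ("event), Kaplan-Meier plots will be used to describe the survival rate of patients without endpoint" events), followed by a log-rank or non-parametric comparison. It names no separate analysis set.

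**Timing of efficacy measures.** Section 3.5.3.1 sets the clinic visits: "Subjects will be followed up at the study center at day" 30 ± 3, 90 ± 7 and 180 ± 7. Section 3.5.3.2 gives the content of the first two: "V2, V4: weight, ALSFRS-R score, grip strength, respiratory function (%FVC), vital signs" and further safety tests. The only earlier scheduled contact is the Day 7 call. On the calls, section 3.5.4.2 says: "The visits (V1, V3, V5 and V6) will be to inquire and teach about treatment compliance in" addition to recording adverse events and concomitant treatment. No efficacy scale is included.

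**Withdrawal visit.** Section 3.5.5 asks subjects who leave early to attend for ALSFRS-R, ALSAQ-40, grip strength and %FVC. The notes to the Trial Schedule place this visit 7 to 14 days after the last dose.

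**The concern.** A time-to-event analysis should start from randomisation and count every subject from then on. Here entry to the analysis depends on something that happens after randomisation, and the event being counted can itself prevent it. A subject who dies in week 3 has had no scheduled efficacy measurement. Read strictly, that subject is outside the FAS, and the death is outside the only efficacy analysis designed to count deaths.

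At stake are the estimated event proportion in each group and the like-for-like comparison of two doses with placebo. With 50 subjects per group and a population selected for good respiratory function, this endpoint will rest on few events, so one lost event changes the result visibly.

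This is not a detail left to the statistical analysis plan. Section 8.3.1 defers the handling of missing values, but section 8.2 itself fixes the FAS definition and its use for efficacy.

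**Working it through.** The protocol makes no sample-size calculation (section 8.1) and states no event rate or dropout rate, so there is no derived figure to reproduce beyond 3 × 50 = 150. The check sets the definition against the visit schedule and then sizes the effect under stated assumptions.

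**Step 1. Who is in the FAS?** Section 8.2 does not say whether an endpoint event is itself a valid efficacy evaluation, so both readings are shown for a dosed subject whose course ends before Visit 2.

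| Course before Day 30 ± 3 | Evaluation means a measured scale, grip or %FVC | An endpoint event also counts |
|---|---|---|
| Leaves, attends withdrawal visit | in | in |
| Leaves event-free, no visit | out | out |
| Ventilated, assessed | in | in |
| Ventilated, not assessed | out, event lost | in |
| Dies before any assessment | out, event lost | in |

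The withdrawal visit matters: a subject whose last dose is on Day 1 could be assessed between Day 8 and Day 15. It cannot help a subject who has died. Under the first reading events are lost. Under the second, early subjects with an event enter and early subjects without one and without a visit do not. Membership depends on outcome under both.

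**Step 2. Effect of one excluded event.** With e events in a group of 50 and x of them excluded, the proportion changes from e/50 to (e − x)/(50 − x). The counts are assumed.

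- e = 2, x = 1: 2/50 = 4.0% becomes 1/49 = 2.0%
- e = 3, x = 1: 3/50 = 6.0% becomes 2/49 = 4.1%
- e = 5, x = 1: 5/50 = 10.0% becomes 4/49 = 8.2%
- e = 3, x = 2: 3/50 = 6.0% becomes 1/48 = 2.1%

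Each excluded event lowers the observed proportion by about 1.8 to 2.0 percentage points.

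**Step 3. How likely is it?** Assume an event rate of 4–6% over 180 days, which is 50 × 0.04 = 2 to 50 × 0.06 = 3 events per group. At a constant hazard the first 30 days hold 30/180 = 1/6 of them: 0.33 to 0.5 per group, or 1.0 to 1.5 in the trial. Not every one of these would be excluded.

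More generally, let p be the probability that a subject is left out for lack of an early evaluation. The expected number is 150p, and the chance of at least one is 1 − (1 − p)^150.

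| Assumed p | Expected of 150 | Chance of at least one |
|---|---|---|
| 0.25% | 0.4 | 31% |
| 0.5% | 0.75 | 53% |
| 1% | 1.5 | 78% |
| 2% | 3.0 | 95% |
| 3% | 4.5 | 99% |

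**Step 4. Could it create a false finding?** Suppose two groups truly have 3/50 each and two early events are excluded from one of them. The report would read 6.0% against 2.1%, Fisher p = 0.62. That is a false numerical difference but not a significant one.

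**The case against.** The other side has real substance.

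- **The text is ambiguous.** Death and ventilation are listed among the efficacy endpoints (section 3.3.1), so event status may be meant as efficacy data. That would keep early events in. It stands as a reason not to call exclusion certain, but Step 1 shows that this reading leaves event-free early leavers out.
- **Early leavers are largely covered.** The withdrawal visit includes the efficacy scales, section 7.2.2 asks for active efforts to complete a last examination, and section 3.5.3.1 allows extra visits. A ventilated subject can also be scored, since ALSFRS-R item 12 (Appendix 2) grades ventilator use. This stands. What remains is early death and non-attendance.
- **Early events should be rare.** Entry requires %FVC of at least 80% and respiratory items at 4 points (section 3.2.1), and the non-invasive ventilation criterion needs at least 10 days. This also stands and limits the size.
- **The trial is exploratory**, and this is one secondary endpoint.

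Two stronger inferences are tempting and are not supported. A reader might infer that early harm is concealed. Deaths from disease progression are not reported as serious adverse events, but section 6.3.3 requires them in the eCRF. The safety set has no efficacy requirement, and the monitoring board in section 9.4 reviews safety data and important effectiveness endpoints. A reader might also infer that exclusions will differ by dose. The healthy-volunteer results in sections 1.2.4 and 1.3.1 report no adverse events leading to withdrawal. Those subjects were healthy, so this does not rule out a difference in patients, but nothing in the protocol shows one.

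**Conclusion.** The point holds in a limited form. Section 8.2 ties every non-per-protocol efficacy analysis to a post-dose evaluation, and section 8.3.4 gives the death, tracheotomy and ventilation endpoint no set of its own. A death before any assessment, or an early ventilation or loss without a withdrawal visit, can therefore fall outside the Kaplan-Meier and log-rank analysis. Exclusion is possible, not certain.

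The number affected is probably small: under the assumed 4–6% event rate and a constant hazard, 1.0 to 1.5 first-month events are expected in the whole trial, and only some would be excluded. The effect per case is not small, at about 2 percentage points in a group of 50. It would be a third to a half of a group's events if that group had only two or three. Those fractions depend on an early event occurring and being excluded, so they are not an expected bias.

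The conclusion about the definition needs no assumed rate; only its size does. The finding concerns the event endpoint, and no effect on the primary Day 180 comparison has been quantified.

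**What to change.** Add one sentence to sections 8.2 and 8.3.4, carried into the statistical analysis plan: the death, tracheotomy and ventilation endpoint is analysed in all randomised subjects (or all randomised and dosed subjects, which is acceptable under blinding), by randomised group, with time counted from randomisation, no requirement for a post-dose evaluation, and event-free leavers censored at last contact.

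Add a second sentence to section 8.3.1, which at present asks for exclusion reasons only for the per-protocol set: list FAS exclusions with reasons, by group.

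The planned ANOVA of the primary endpoint in section 8.3.3 can stay as it is for this purpose. The cost is a text amendment and one extra listing. Deaths and contact dates are already to be recorded, so no new data are needed.

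### The Per-Protocol Set requires completed treatment, but an endpoint event forces treatment to stop, so the set excludes on-treatment endpoint events by construction

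*Protocol*

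**What the plan says.** Protocol section 8.2 defines the PPS as FAS subjects who satisfy the main inclusion criteria, do not "meet the main exclusion criteria, complete the treatment without any major protocol deviations". It makes no exception for subjects whose treatment ended because of an efficacy event. On purpose, it says: "The PPS is mainly used for the sensitivity analysis of efficacy". No endpoint is left out of that role.

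The FAS has a different rule. It needs randomisation, one "administration and at least one valid post-dose efficacy evaluation data. FAS is the primary" analysis set. Completion of treatment is not required.

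The Synopsis, under treatment termination, is worded as an obligation: "Subjects need to terminate the treatment permanently if the following events occur". Among the events is a medical emergency that requires ending "treatment permanantly, such as death, tracheotomy, invasive ventilator assisted ventilation, or continuous non-invasive ventilator assisted ventilation", with the non-invasive case limited to at least 22 h per day for at least 10 days.

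Section 8.3.4 lists the first secondary endpoint as "Proportion of endpoint events, including death, tracheotomy, invasive ventilator-assisted" ventilation, or continuous non-invasive ventilation at the same threshold. It plans Kaplan-Meier plots and a log-rank or non-parametric comparison.

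Section 7.2.1 is softer on one of these events. For dependence on a ventilator at the same hours and days it says "and the investigator decides whether the subject withdraws from the" trial.

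**The concern.** A per-protocol set is meant to drop subjects whose conduct departed from the protocol. Here a subject can take every dose, have an endpoint event on Day 100, stop treatment because the protocol requires it, and be excluded for not completing. Adherence plays no part in that exclusion; the efficacy outcome causes it.

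Two consequences follow. For the event endpoint, the PPS has lost the events it is supposed to analyse. For the continuous endpoints, it loses fast progressors, and more of them from the arm that progresses faster, which pulls a true benefit towards zero. Section 3.1.4 says the trial is to support a phase 3 study. An event-free PPS, or close agreement between FAS and PPS, could then be read as evidence of robustness when it partly reflects how the set was built.

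**Working it through.** **Inputs from the protocol.** 150 subjects, 50 per arm (section 8.1); 3 × 50 = 150, which agrees. Section 8.1 makes no statistical assumptions, so there is no event rate, SD or power to reproduce. Section 3.1.1 cites a 2.5-point ALSFRS-R difference over 6 months for edaravone. It is used below only as an illustrative effect size.

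**Step 1: the definitions side by side.**
- PPS membership requires completed treatment (8.2).
- An endpoint event requires permanent treatment termination (Synopsis).
- The terminating events and the components of the first secondary endpoint are the same list, with the same ventilation threshold (Synopsis, 8.3.4).

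So an endpoint event before the end of treatment implies non-completion, which implies exclusion from the PPS. This step needs no assumed figure.

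**Step 2: the event endpoint.** With an assumed 180-day event rate p, expected events in 150 subjects are 150 × p, and the chance of at least one is 1 − (1 − p)^150.

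| Assumed p | Expected events in 150 | Chance of at least one | On-treatment events in PPS, literal reading |
|---|---|---|---|
| 2% | 3 | 95% | 0 |
| 5% | 7.5 | over 99.9% | 0 |
| 10% | 15 | over 99.9% | 0 |
| 20% | 30 | over 99.9% | 0 |

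With no events, every PPS proportion is 0% and the log-rank statistic is 0/0, so it cannot be computed. That holds whatever the drug does.

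**Step 3: ALSFRS-R.** This was simulated with 1,000,000 subjects per arm. All inputs are assumptions.
- Control change Y ~ N(−7.5, SD²) and active change Y ~ N(−5.0, SD²), a true difference of 2.5, with SD 5 or 6. The level −7.5 cancels from the difference.
- Event liability L = ρ(Y + 7.5)/SD + √(1 − ρ²)·Z, with Z standard normal and ρ = 0.5 or 0.8.
- An event occurs when L falls below the cut that gives the stated control rate. The same cut applies to the active arm.
- PPS difference = mean Y of event-free active subjects minus mean Y of event-free control subjects.

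| Control event rate | Active event rate | PPS difference (true value 2.5) |
|---|---|---|
| 2% | 0.7-1.2% | 2.38-2.46 |
| 5% | 2.0-3.2% | 2.26-2.40 |
| 10% | 4.6-6.9% | 2.11-2.33 |
| 20% | 10.7-14.7% | 1.91-2.27 |

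The loss is 0.04-0.12 points at 2%, 0.10-0.24 at 5% and 0.17-0.39 at 10%. The simulation gives every subject a Day 180 value, including those with events. In the trial, subjects who die will have none, so the real gap between FAS and PPS also depends on the missing-data rule.

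**The case against.** The case on the other side is substantial.

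- **The FAS is primary and does not require completion.** This stands. Excluding subjects from the PPS does not change the main efficacy result.
- **The PPS remains usable for most endpoints.** A reader might infer that it cannot test any efficacy result. The documents do not support that. ALSFRS-R, grip strength, %FVC and ALSAQ-40 can all be estimated in it, with mild bias when events are few. Entry limits such as %FVC of at least 80% may keep them few.
- **No section says outright that the Kaplan-Meier and log-rank analysis will be repeated in the PPS.** True, but 8.2 assigns the PPS to efficacy sensitivity analysis without exempting any endpoint.
- **Not every ventilated subject is excluded.** This stands. Only invasive ventilation, or non-invasive ventilation at the stated threshold, triggers termination, and an event after the last dose excludes nobody.
- **Section 7.2.1 leaves ventilator dependence to the investigator.** That concerns withdrawal from the trial, whereas the Synopsis concerns treatment, and it does not change the position for deaths. If discretion did govern, PPS membership after an event would rest on an individual judgement. The two texts need reconciling.
- **The SAP may define completion, and section 8.3.1 requires reasons for PPS exclusion to be listed.** Listing makes the exclusions visible but does not undo the selection. An SAP that kept these subjects would depart from the literal wording of 8.2, which would still need aligning.

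A reader might also size the bias by how far one arm's mean moves when its event subjects are dropped, and set that against the 2.5-point benchmark. That compares a one-arm shift with a between-arm difference, and it assumes Day 180 values that subjects who died cannot have.

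**Conclusion.** The concern holds in a limited form. Taken literally, section 8.2 and the Synopsis together exclude from the PPS every subject with an on-treatment endpoint event. For the event endpoint, a PPS sensitivity analysis is therefore uninformative; this follows from the definitions alone. For the continuous endpoints the PPS is selected on outcome but still analysable. Under the assumed difference of 2.5, SD 5-6 and correlation 0.5-0.8, the ALSFRS-R estimate falls to about 2.4-2.5 at a 2% control event rate, 2.3-2.4 at 5% and 2.1-2.3 at 10%. None of those rates, SDs or correlations is in the protocol. The primary FAS analysis is unaffected. This should be corrected because a stated rule produces the problem and the correction is cheap, but it does not threaten the main result.

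**What to change.** In section 8.2, replace the completion requirement with adherence up to a defined point: study treatment taken without major protocol deviation until Day 180 or the first endpoint event (death, tracheotomy, invasive ventilation, or continuous non-invasive ventilation at the protocol threshold), whichever is earlier. Add that termination required by the protocol because of such an event counts neither as non-completion nor as a deviation.

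State that Day 180 values are handled by the same missing-data rule in the PPS as in the FAS. Without this, keeping a subject up to the event adds no Day 180 change, and the ALSFRS-R estimate in the PPS may not move.

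If the sponsor prefers a completers-only PPS, say that it will not be used for the event endpoint.

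Separately, reconcile the Synopsis (treatment must end) with section 7.2.1 (investigator decides on withdrawal) for ventilator-dependent subjects, so that classification after an event does not depend on which text is applied.

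The cost is a few sentences in 8.2, matched in the SAP, plus the reconciliation. It needs no new data or visits. The PPS becomes slightly larger and may look less favourable.
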